# 2. Schedule of Activities

Study Schedule Protocol J1X-MC-GZHA – for Subcutaneous Cohorts

Procedure	Screening				ment Period:	SC (	Coho	rt				Fo	llow-	up	Comments/ Notes
Days	-28 to -2	-2	-1	1	2	3	4	5	6	8	15	29	43	ET	
2 1 1 2											± 1	± 3	± 3		
Study informed consent	X														
Medical history	X														
Physical examination/ Medical assessment	X		X	P	X			X	X	X	X	X	X	X	Complete physical examination at screening. Symptom-directed physical examination across study at other timepoints.
Height and weight	X			P						X	X	X	X	X	Height at Screening only.
Confirmation of eligibility followed by randomization		X													
Admit to CRU		X													
Discharge from CRU – on completion of inpatient procedures							X								Participants may remain inpatient longer than Day 4, at the investigator's discretion.
Administer study drug				X											Refer to Section 7.1.
AEs/ concomitant medications	X		X	X	X	X	X	X	X	X	X	X	X	X	
Vital signs: supine BP and PR (h)	X			P, 1, 4, 6, 12	24	48	72	96	120	168	X	X	X	X	For Day 15 and subsequent visits, vital signs should be measured within 30 min of the scheduled PK sample.
Body temperature (h)	X			P, 6, 12	24										
ECG – single	X											X	X	X	

Procedure	Screening			Treat	ment Period:	SC (	Coho	rt				Fo	llow-	-up	Comments/ Notes
Days	-28 to -2	-2	-1	1	2	3	4	5	6	8	15	29	43	ET	
ECG – triplicate (m, h)				-30m, -15m, 0, 1, 4, 6, 12h	24	48	72	96	120	168	X X	±3	±3		Day 1 Predose ECGs will be taken in triplicates at - 30, -15 and 0 min to establish a baseline. Day 15 ECG should be measured within approximately 30 min of the PK sample.
Clinical safety lab tests (fasted)	Х			P	Х		X			X	X	X	X	X	
Serology  • Hepatitis B surface antigen, Hepatitis B core antibody  • Hepatitis C antibody  • HIV	Х														
Point of care safety glucose samples				Pre-n lun	Days 1 – 3: neals (breakfa ch and dinner before bedtim	)	X	X	X						Days 4 -6: Fasted samples collected before breakfast.
PK sampling (h)				P, 6, 12	24	48	72	96	120	168	X	X	X	X	Days 15, 29, 43 and ET: Samples collected anytime during visit. The ET sample is not required for participants who discontinued without receiving IP.
OGTT – 75 g glucose challenge (h)			X		24										Conducted following overnight fast.

Procedure	Screening			Treat	ment Period:	SC (	Coho	rt				Fo	llow-	up	Comments/ Notes
Days	-28 to -2	-2	-l	1	2	3	4	5	6	8	15	29	43	ET	
											±1	±3	±3		
PD biomarkers (h):			Pre-OGTT,	P	Pre-OGTT,	48	72			X	X	X			Days 1, 3, 4, 8, 15 and 29:

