9.5.5 Vital signs

Vital signs data will be summarized by treatment group together with changes from baseline, where baseline is defined as the Day 1 predose assessment. Figures of mean vital signs and mean changes from baseline profiles will be presented by treatment.

Values for individual subjects will be listed.

For change from baseline values, a mixed-model repeated-measure model with treatment, time (of measurement), and treatment-by-time interaction as fixed effects, subject as a random effect, and baseline as covariate will be used to determine the effects of LY3493269. Least-squares means as well as 90% CIs for the difference of LY3493269 compared with placebo will be

reported. An unstructured covariance structure will be used and a compound symmetry structure may be used if this fails to converge.

Example of SAS code (for the change from baseline analysis) as follows.

```
proc mixed data=xxx;
class treatment timepoint subject;
model change = baseline treatment timepoint treatment*timepoint
/residual ddfm=kr;
repeated timepoint / subject=subject type=UN;
lsmeans treatment*timepoint / cl pdiff alpha=0.1;
ods output lsmeans=lsm diffs=estims;
run;
```

The relationship between the time-matched LY3493269 concentrations and changes from baseline and mean time-matched placebo for all vital signs parameters will be explored graphically using a scatter plot. A regression analysis using a linear mixed-effects model will be performed. A plasma LY3493269 concentration- vital signs data analysis will be performed to assess the changes from baseline (Day 1 predose) and mean time-matched placebo for each vital sign relative to plasma LY3493269 concentrations across all active treatments. The change from baseline adjustment will be based on each individual subject's Day 1 predose value, and an additional placebo adjustment will be based on mean time-matched placebo values. The analysis will be performed by plotting double delta vital signs measurement against LY3493269 concentration as a covariate. The estimated regression line and associated 90% CI will be fitted on the plot and the p-value for the slope reported. Estimated delta vital signs result and 90% CI at the geometric mean C_{max} will also be presented.

Example of SAS code as follows:

```
proc mixed data=xxx;
  class subject;
  model DDchg = concentration / solution cl alpha=0.1 ddfm=kr;
  random subject;
  ods output estimates=est;
  ods output solutionf=sol;
run;
```

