9.5.6 Electrocardiogram (ECG)

The ECG data will be obtained directly from the 12-lead ECG traces. These data include the PR, QT, RR, QRS duration and heart rate. In addition, QT interval corrected using Fridericia's formula (QTcF) will be calculated as follows:

$$QTcF = \frac{QT}{\sqrt[3]{60/HR}}$$

The mean of triplicate data will be used for reporting. The ECG data will be summarized by treatment group together with changes from baseline, where baseline is defined as the mean of the triplicate Day 1 predose assessments (-30, -15 and 0 minute). Figures of mean ECG data and mean changes from baseline will be presented by treatment. The frequency of subjects with a maximum increase from baseline in QTcF interval will be summarized for each treatment according to the following categories: >30 ms and >60 ms. In addition, the frequency of subjects QTcF postdose values, according to the following categories: >450 ms, >480 ms and >500 ms, will be summarized by treatment.

The relationship between the time-matched LY3493269 concentrations and changes from baseline and mean time-matched placebo on QTcF will be explored graphically using a scatter plot. A regression analysis using a linear mixed-effects model will be performed. A plasma LY3493269 concentration-QTcF analysis will be performed to assess the changes from baseline (Day 1 predose) and mean time-matched placebo in the QTcF interval relative to plasma LY3493269 concentrations across all active treatments. The change from baseline adjustment will be based on each individual subject's Day 1 predose value, and an additional placebo adjustment will be based on mean time-matched placebo values. The analysis will be performed by plotting double delta QTcF against LY3493269 concentrations, including all post dosing timepoints. A linear mixed-effects model will be performed on the double delta QTcF values and will include LY3493269 concentration as a covariate. The estimated regression line and associated 90% CI will be fitted on the plot and the p-value for the slope reported. Estimated delta QTcF and 90% CI at the geometric mean C_{max} will also be presented. The analysis will also be produced for heart rate and PR.

Example of SAS code as follows:

```
proc mixed data=xxx;
  class subject;
  model DDchg = concentration / solution cl alpha=0.1 ddfm=kr;
  random subject;
  ods output estimates=est;
  ods output solutionf=sol;
run;
```

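### The concentration-response models subtract the Day 1 predose value but do not adjust for it, which costs some precision for blood pressure and pulse and little for the ECG measures

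*SAP*

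**What the plan says.** SAP 9.5.6 regresses double-delta QTcF on concentration: "A linear mixed-effects model will be performed on the double delta QTcF values and will include LY3493269 concentration as a covariate". It names no other fixed effect, and "The analysis will also be produced for heart rate and PR". SAP 9.5.5 specifies the same regression for the vital signs. The example code in both sections is "model DDchg = concentration / solution cl alpha=0.1 ddfm=kr", with a random subject effect.

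Baseline enters only through the response: "The change from baseline adjustment will be based on each individual subject's Day 1 predose value". The mean of the placebo participants at the same time is then subtracted as well.

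The baselines differ in quality. For ECG, "baseline is defined as the mean of the triplicate Day 1 predose assessments (-30, -15 and 0 minute", in line with the Protocol's schedule: "Day 1 Predose ECGs will be taken in triplicates at - 30, -15 and 0 min to establish a baseline". For vital signs, "where baseline is defined as the Day 1 predose assessment", which is a single assessment. Both the SC and the IV schedule in Protocol section 2 include these readings for every participant.

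The MMRM for vital-sign change, also in SAP 9.5.5, does adjust for baseline: "subject as a random effect, and baseline as covariate will be used to determine the effects of LY3493269". The SAP gives no reason for treating the two models differently. Protocol 10.3.1.2 lists baseline as a covariate in the MMRM and lists no covariates for the QTcF concentration analysis.

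**The concern.** Subtracting a noisy baseline carries its error into every change score of that participant. In a random-intercept model the error ends up in the between-participant variance. A baseline covariate removes part of it.

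These regressions yield the slope p-value and the 90% CI at geometric mean Cmax. They do so for effects the Protocol treats as an identified risk: sections 3.3 and 5.5 cite heart-rate and blood-pressure increases in monkeys. With six active participants per dose, precision that can be had from data already collected is worth having.

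**Working it through.** **Planned size.** 6 SC cohorts × 8 + 6 IV = 54, the SAP's completer figure. Active: 6 × 6 + 6 = 42. Placebo: 6 × 2 = 12. The documents give no power, SD, correlation or precision target for these models, so everything below rests on assumed variances.

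**What a covariate can remove.** Take unit variance for one reading, with between-participant part ρ and within-participant part 1−ρ, and a baseline that averages k readings.

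- Baseline reliability: r = ρ / (ρ + (1−ρ)/k).
- Baseline error carried into the change score: (1−ρ)/k.
- The same after adjustment: r(1−ρ)/k. The SD of this component therefore falls by the factor √r.

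| ρ | √r, one reading (k = 1) | r, three readings (k = 3) | √r, three readings |
|---|---|---|---|
| 0.3 | 0.55 | 0.3/(0.3+0.233) = 0.56 | 0.75 |
| 0.5 | 0.71 | 0.5/(0.5+0.167) = 0.75 | 0.87 |
| 0.7 | 0.84 | 0.7/(0.7+0.1) = 0.875 | 0.94 |

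Averaging three readings also cuts the error to be removed to a third. The effect at Cmax carries other error too, so the gain in its standard error is smaller than √r suggests.

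**Simulation A: SE at the 7.5 mg Cmax.** 36 SC active and 12 placebo participants. One-compartment PK scaled to Table GZHA.2 (AUC 7670 ng.h/mL and Cmax 31.2 ng/mL at 0.15 mg), dose-proportional, with assumed ka 0.05/h and 30% CV. The table gives true SE with baseline divided by true SE without it.

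| Setting | ρ = 0.3 | ρ = 0.5 | ρ = 0.7 |
|---|---|---|---|
| Covariate added to double-delta model, one reading, vital-sign times | 0.87 | 0.92 | 0.95 |
| Same, one reading, ECG times | 0.81 | 0.89 | 0.94 |
| Same, three independent readings, ECG times | 0.91 | 0.94 | 0.98 |
| Placebo change adjusted too, one reading, vital-sign times | 0.74 | 0.84 | 0.91 |
| Placebo change adjusted too, three independent readings, ECG times | 0.84 | 0.94 | 0.97 |

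With the covariate alone, one reading gives reductions of 5-13% at the vital-sign times and 6-19% at the ECG times. Three readings give 2-9%.

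**Simulation B: assumed SDs, REML fits.** Nine paired PK/ECG times and 2,000 trials per setting. The ratios are for true SD with and without baseline, with placebo participants in the model.

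- Vital signs, between/within SD 8/6: r = 64/(64+36) = 0.64, ratio 0.90. SD 7/7: r = 0.50, ratio 0.82.
- QTcF, 15/6 ms, three readings: r = 225/(225+12) = 0.95, ratio 0.99-1.00. If the three predose readings act as one: 0.97, or 0.91 at 12/8 ms.
- Heart rate, 8/5 bpm: 0.985 with three readings, 0.92 if they act as one.
- PR, 18/5 ms: r = 324/(324+8.3) = 0.97, ratio 0.99-1.01.

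**Why the placebo participants belong in the model.** In simulation B, baseline was also added to the double-delta model alone, centred on the active participants. For vital signs the printed SE fell from 1.98 to 1.84 (7%) and from 2.28 to 2.01 (12%). The true SD fell only from 3.32 to 3.23 (3%) and from 3.79 to 3.60 (5%). The nominal 90% CI covered 68-76% without the covariate and 66-75% with it, because the mean of at most 12 placebo participants is treated as known. With placebo participants in the model, coverage was 89-92%.

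**Limits.** The 6 IV participants were not simulated, and errors were taken as independent across occasions.

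**The case against.** The strongest reply is that baseline is already used, since every response is a change from the participant's own predose value. That is correct. A reader might infer that the plan ignores baseline, but the documents do not support this. Only the adjustment for what subtraction leaves behind is missing.

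The second reply is that the gain is weakest in the ECG section. This also stands. Averaging three predose triplicates leaves little error to remove, and for PR almost none. A reader might carry the blood-pressure figure over to QTcF, but that would model a single-reading baseline, which the SAP does not use for ECG.

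The third is that little depends on these outputs. The primary endpoints are TEAEs and SAEs. Blood pressure and pulse already have a baseline-adjusted MMRM against placebo. QTcF has categorical outlier summaries. Protocol 7.4.1 bases escalation primarily on safety data, and no decision rule uses these regressions. This limits the severity. It does not explain why two models for the same vital-sign changes treat baseline differently.

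**Conclusion.** The point holds in limited form. The covariate is absent from both concentration-response models, and adding it would use data already scheduled for everyone. The loss in true SE at geometric mean Cmax is about 5-20% for blood pressure and pulse over assumed correlations of 0.7 to 0.3. It is about 0-10% for QTcF and heart rate, and probably near zero for PR.

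These ranges depend on the assumed variances. Adjusting the placebo change as well gives more at low correlation (26% for vital signs and 16% for ECG at 0.3). Centring on the active participants alone gives less (3-5% for vital signs). The ECG range assumes largely independent errors in the predose readings. If those readings, taken within 30 minutes, share their error, the ECG gain moves towards the single-reading figures.

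A reader might turn the loss into lost power. The documents do not support that: the study is not powered on any hypothesis test, and no effect size is stated from which power could be computed. Severity is minor.

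**What to change.** In SAP 9.5.5 and 9.5.6, fit one model to active and placebo participants together. The response is change from baseline. The fixed effects are nominal time, an active/placebo indicator, concentration (0 for placebo) and the Day 1 predose value centred on the mean of all participants in the analysis. Subject is a random effect. For example, with `active` coded 0/1:

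`class subject time; model chg = time active conc cbase / solution cl alpha=0.1 ddfm=kr; random subject;`

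Report the effect at geometric mean Cmax as the `active` coefficient plus slope × Cmax, with its 90% CI, at centred baseline = 0. In this additive model the placebo-adjusted effect is the same at any baseline; the centring fixes the level of any fitted change that is plotted. Do not simply add the term to the double-delta model.

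The SAP should also say how IV readings at nominal times without a placebo reading (for example 8 h) enter the model. If the sponsor prefers to keep baseline out, a sentence of justification is enough for the ECG intervals but less convincing for blood pressure and pulse.

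Cost: one covariate and a changed model statement in two sections. No new data are needed, and there is no conflict with Protocol 10.3.1.2, which leaves the covariates of the QTcF concentration analysis open.

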9.5.7 Immunogenicity Assessments

The frequency and percentage of subjects with pre-existing antidrug antibody (ADA) and with treatment-emergent ADAs (TE ADA) to LY3493269 may be tabulated and listed if available.

For subjects who are ADA negative at baseline, TE ADAs are defined as those with a signal increase, greater than assay variability, compared to baseline. The frequency of cross-reactive binding to native GIP, GLP-1 or neutralizing antibodies may also be tabulated in TE ADA+ participants, when available.

9.5.8 Injection-Site Reactions

Injection-site assessments for local tolerability will be conducted, when reported as

• an AE from a subject, or

• a clinical observation from an investigator.

Reported injection-site reactions will be characterized within the following categories:

- edema
- erythema
- induration
- pruritus
- pain

In case of an AE of injection-site reaction, pain data will be listed.

Injection-site reaction data will be listed and summarized by treatment in frequency tables.

9.5.9 Appetite Analysis

To explore the effects of LY3493269 on meal intake and appetite sensation, subjects will be asked to rate their appetite sensations using a 100-mm visual analog scale (VAS) for parameters of hunger, fullness, satiety, and prospective food consumption prior to dosing on Day 1, and in the fasted state while inpatient as well as on scheduled outpatient visits.

The VAS is presented as a 10-cm (100-mm) line, anchored by verbal descriptors, usually "extremely" and "not at all". Subjects are required to rate their subjective sensations on four 100 mm scales combined with questions similar to the following:

- 1. "How hungry do you feel?"
- 2. "How satisfied do you feel?"
- 3. "How full do you feel?"
- 4. "How much do you think you could eat?"

A staff member will use a caliper to measure the distance from 0 to the mark that the subject placed on the VAS and record the measurement in the source document. Overall appetite score is calculated as the average of the 4 individual scores: [satiety + fullness + (100-prospective food consumption) + (100-hunger)] / 4.

The individual VAS measurements and overall appetite score will be listed and summarized by treatment and timepoint, alongside change from baseline (Day 1 predose).

The individual parameters, and overall score, will be analyzed using an MMRM model to evaluate treatment effects as well as treatment comparisons. The model will include treatment, timepoint, and treatment-by-timepoint interaction as fixed effects, and subject as a random effect. An unstructured covariance structure will be used and a compound symmetry structure may be used if this fails to converge. Least-squares means as well as 90% CIs for the difference of LY3493269 compared with placebo will be reported. The distribution of the data will be tested prior to analyses and should the distribution indicate a parametric analysis not to be

appropriate, a non-parametric analysis will be used instead. Change from baseline (Day 1 predose) will also be analysed, with a covariate for baseline added to the model.

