5. STUDY DESIGN

Study GZHA is a Phase 1, single-site, randomized, placebo controlled, single-ascending dose (SAD) study in healthy participants, to evaluate the safety, tolerability, and PK of LY3493269 administered as single SC doses and as a single IV dose. The PD effects of SC doses of LY3493269 on glycemic effects (including fasting glucose, insulin, and glucose and insulin during an oral glucose tolerance test [OGTT]) and appetite will be explored. For the SC cohorts, the investigator and participants will be blinded. The IV Cohort is open label with no placebo.

The planned LY3493269 SC doses for this study range from 0.15 mg to 7.5 mg. These dose levels may be adjusted (for example, dose increments may be reduced, a dose level may be repeated, or a lower/intermediate dose may be administered) based on ongoing review of available safety, tolerability, PK, and PD data. Any proposal to adjust SC or IV doses from those planned and stated in the protocol, together with supporting data, will be reviewed by an independent safety review panel.

Participants will undergo safety (including but not limited to adverse events [AEs], medical assessments, clinical laboratory tests, body weight, vital signs and ECGs]), PK and PD assessments.

Subcutaneous Administration Cohorts 1 through 6

This study includes up to 6 planned SC cohorts:

- SC Cohort 1: 0.15 mg (6 LY3493269: 2 Placebo)
- SC Cohort 2: 0.5 mg (6 LY3493269: 2 Placebo)
- SC Cohort 3: 1.5 mg (6 LY3493269: 2 Placebo)
- SC Cohort 4: 3.0 mg (6 LY3493269: 2 Placebo)
- SC Cohort 5: 5.0 mg (6 LY3493269: 2 Placebo)
- SC Cohort 6: 7.5 mg (6 LY3493269: 2 Placebo)

Cohorts 2 to 6 will be initiated only if the investigator and Eli Lilly and Company clinical pharmacologist deem the safety results in the preceding cohort to be acceptable through Day 8 from at least 6 participants dosed. In addition, all planned participants in the current cohort should have been dosed prior to escalation to the next cohort.

Intravenous Administration Cohort

This study includes a single IV cohort (IV Cohort), where up to 6 healthy participants should complete dosing at the same level to provide sufficient PK sampling. The IV Cohort will be initiated based on review of safety and tolerability data from SC Cohort 3 and available 7-day PK data and/or PD data from at least 2 preceding SC cohorts.

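### SAP 9.5.9 lets an unspecified distribution test replace the appetite MMRM with an unnamed non-parametric analysis that has no stated estimate or CI

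*SAP*

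**What the plan says.** SAP 9.5.9 sets out the model first: "The individual parameters, and overall score, will be analyzed using an MMRM model to evaluate treatment effects as well as treatment comparisons". The planned output is "Least-squares means as well as 90% CIs for the difference of LY3493269 compared with placebo will be reported". A failure of the covariance structure has a named fallback: "An unstructured covariance structure will be used and a compound symmetry structure may be used if this fails to converge".

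The next sentence makes the whole analysis conditional. It opens with "The distribution of the data will be tested prior to analyses and should the distribution indicate a parametric analysis not to be", and its remainder provides that, where the parametric approach is judged unsuitable, "a non-parametric analysis will be used instead". Only after that does the section add that change from Day 1 predose is also analysed, with baseline as a covariate.

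The section does not say:
- which test is used, or at what level;
- whether raw scores, changes or residuals are tested;
- whether values are pooled, taken by timepoint or taken by arm;
- which non-parametric method follows;
- what estimate or interval that method would report.

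The MMRMs for fasting glucose, insulin and C-peptide (SAP 9.4.1), vital signs (9.5.5) and body weight (9.5.10) have no such condition. Protocol 10.3.3.2, which covers PD parameters without naming appetite, plans mixed-effects models. It allows transformation and mentions no non-parametric switch. Protocol Table GZHA.1 defines the appetite endpoint as a change in VAS score in the fasted state.

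**The concern.** The method would be settled after the data are seen, by a check whose result depends on how it is run. Scores lie on a bounded line ("The VAS is presented as a 10-cm (100-mm) line, anchored by verbal descriptors"). Pooling them over arms and days mixes groups with different means, so the pooled values can look non-normal even when the model's residuals are acceptable. A test within one arm of 6 usually has little power. Neither result says much about whether the model's intervals can be trusted.

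If the switch is made, no replacement is promised for the difference from placebo, its 90% CI, the baseline adjustment or the treatment-by-time structure. The one rank method that the SAP names, Kruskal-Wallis for tmax in 9.3.2, has only a p-value as its stated inferential output. Applied score by score, the rule could also leave the four scales and their average analysed by different methods, which makes them hard to read together.

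**Working it through.** **Inputs from the documents.** Each SC cohort is 6 active to 2 placebo (for Cohort 1, "SC Cohort 1: 0.15 mg (6 LY3493269: 2 Placebo"). Six cohorts give 6 × 6 = 36 active and 6 × 2 = 12 placebo, so N = 48. SAP Section 6 treats placebo as one group. With the IV cohort, 6 × 8 + 6 = 54, which reproduces the planned number of completers. The SC schedule in Protocol Section 2 shows 7 VAS times (Day 1 predose, 24 h, 48 h, Days 5, 8, 15 and 29), so one scale yields 48 × 7 = 336 pooled values.

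**Assumptions, because the documents give no VAS mean, SD, correlation, effect or test.** Scores on 0–100 are either beta-distributed or normal clipped at the bounds. Within-participant correlation is 0.5. Any effect falls linearly with dose rank to the stated top-dose value and is the same at all postdose times. The test is Shapiro-Wilk at 5%. There are 600 runs per setting, so the simulation SE of a rejection rate is at most √(0.25/600) = 2.0 percentage points.

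**Interval checked.** For absolute scores at each postdose time:

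difference ± t(0.95; 48 − 7 = 41 df) × s × √(1/6 + 1/12), where √(1/6 + 1/12) = √0.25 = 0.5

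Here s is the SD pooled over the seven arms. With complete data this matches the saturated unstructured MMRM. Change scores used an ANCOVA on baseline at each time (48 − 8 = 40 df), which is close to the SAP model but not identical to it. Coverage was taken for the lowest and highest doses against placebo.

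**Results** (rejection in %; the by-time column is the average over the 7 times; coverage is absolute / change):

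| Setting (mean, SD, top-dose effect in mm) | Pooled raw | Pooled residuals | By time | Pooled change | 90% CI coverage |
|---|---|---|---|---|---|
| Beta 50, 25, none | 100 | 91 | 29 | 13 | 0.902 / 0.900 |
| Beta 30, 20, none | 100 | 100 | 78 | 28 | 0.907 / 0.907 |
| Beta 60, 19, 30 | 98 | 33 | 11 | 19 | 0.904 / 0.905 |
| Beta 50, 15, none | 37 | 19 | 4 | 10 | 0.897 / 0.895 |
| Beta 50, 15, 20 | 69 | 30 | 7 | 14 | 0.903 / 0.900 |
| Clipped 60, 25, 30 | 100 | 27 | 9 | 17 | 0.911 / 0.909 |
| Clipped 50, 20, none | 18 | 10 | 3 | 8 | 0.898 / 0.897 |
| Clipped 50, 15, none | 10 | 10 | 5 | 12 | 0.905 / 0.906 |
| Overall score: four beta scales, 60, 22, 30 | 73 | 12 | 5 | 42 | 0.903 / 0.902 |
| Overall score: four beta scales, 50, 19, none | 12 | 12 | 4 | 10 | 0.901 / 0.904 |

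Across all 14 settings run, pooled raw single scales rejected in 10–100% and pooled change in 8–42%; the 42% is for the overall score. Further runs with other assumed values took the pooled raw figure down to 8%. The overall-score rows treat the four scales as independent, which favours normality.

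**Three readings of the results.**
1. The testing unit decides the outcome. In the clipped 60, 25, 30 setting the same trials fail 100%, 27%, 9% or 17% of the time, depending only on what is tested.
2. The drug effect itself raises rejection of pooled raw scores: 37% to 69% at SD 15 in the table. In separate clipped-normal runs (mean 50, SD 22, 1,500 runs, six postdose times), rejection was 32% with no effect, 76% with 20 mm and 99.9% with 40 mm. By timepoint it was 4%, 4% and 25%.
3. Coverage stayed at 0.895–0.911 in all 14 settings, including those where the pooled test always rejected.

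**The case against.** The text refers to the distribution of the data and to a parametric analysis being unsuitable. It does not mention pooling, a 5% level or an automatic trigger, so a sensible statistician could look at residuals and use judgement. This stands. A reader might infer that bounded VAS data are bound to fail the test, but the documents do not support that: for pooled change from baseline, the protocol's endpoint, rejection was only about 8–42%.

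A reader might also infer that the model's intervals are valid whatever the data look like. That goes too far as well. The intervals rest on a common variance across arms. With placebo and low doses near the ceiling (mean 80–85, SD 10–12) and a mixed-response top dose (mean 40–45, SD 30–32), simulated coverage of the top-dose interval fell to 69–75%. With a third to two thirds of the top-dose group at the floor it was conservative, at 0.937–0.967. Unease about a parametric model with 6 per dose is therefore reasonable. A normality test is not a reliable remedy for unequal spread, however.

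Nor do the documents say that only a p-value would remain. Rank methods can give a shift estimate and an interval; the SAP simply commits to neither. Descriptive summaries of scores and changes by treatment and timepoint are not conditional on the test. Because the change analysis is described after the test, the condition could even be read as covering absolute scores only, in which case the baseline-adjusted results would survive. The section does not settle this.

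**Conclusion.** The point holds as a minor one. An unspecified preliminary test can remove the promised differences and 90% CIs, and can split the five scores between methods, for a reason that in these simulations did not track whether the intervals were sound. Rejection ranged from roughly 8% to 100% for pooled raw single scales and from about 8% to 42% for pooled change, so the switch is possible and sometimes likely, but not certain. Coverage near 90% applies to complete data with similar spread across arms. All VAS means, SDs, correlations and effects are assumptions. Appetite is an exploratory objective in a study not powered for hypothesis tests, and the primary safety and secondary PK results do not depend on this analysis.

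**What to change.** In SAP 9.5.9, delete the distribution test and the substitution. State that the MMRM is the reported analysis for all four scales and the overall score, with baseline as covariate for change. State that residuals and spread by arm will be checked graphically. If these look poor, add to the MMRM, and do not substitute for it, one sensitivity analysis named in advance with its estimate and 90% CI. A Hodges-Lehmann shift from placebo at each timepoint would serve, as would a permutation analysis stratified by cohort. Neither fully cures unequal spread, so report the spread plots alongside.

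The cost is a few sentences of SAP text and possibly one extra table. Data collection and study conduct do not change.
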